2.3 Rationale

In an ongoing Phase 1/2, multicenter, open-label study evaluating the safety and clinical efficacy of the PD-L1 monoclonal antibody durvalumab 10 mg/kg IV every 2 weeks in patients with multiple solid tumor types including NSCLC, the ORR in NSCLC was 14% (23% in patients with PD-L1+ tumors by the SP263 Ventana PD-L1 immunohistochemistry test), and the disease control rate (DCR) at 24 weeks was 24% (Rizvi et al. 2015). ORR was higher in squamous (21%) than in non-squamous patients (10%), and responses were durable. Drug-related adverse events (AEs) were reported in 48% of patients and were most frequently fatigue (14%), decreased appetite (9%), and nausea (8%). Grade ≥ 3 drug-related AEs were reported in 6% of patients. Recently, several phase I/II clinical trials have evaluated the clinical activity of monotherapy with PD1 and PD-L1 blocking antibodies in the 1st line treatment of advanced NSCLC. These clinical trials indicate early evidence of durable antitumor activity with response rates of 23-29% and tolerable toxicity profiles similar to what has been previously demonstrated. There are currently several ongoing randomized phase III clinical trials evaluating PD1 and PD-L1 blocking antibodies in the 1st line treatment of advanced NSCLC. MYSTIC is a phase III open-label study of 1st line durvalumab (20 mg/kg IV every 4 weeks) with or without a monoclonal antibody to CTLA-4, tremelimumab (1 mg/kg IV every 4 weeks for up to 4 doses), vs. standard of care chemotherapy in advanced NSCLC (NCT02453282.) Notably, this clinical

HCC #:16-054

Version Date: 008/11/2020

trial is being conducted in patients with an Eastern Cooperative Oncology Group (ECOG) performance status of 0 or 1.

An ECOG performance status of 2 (PS2) is defined as being “ambulatory and capable of all self-care but unable to carry out any work activities; up and about more than 50% of waking hours” (Oken et al. 1982). Up to 30 to 40% lung cancer patients present with an ECOG PS2 (Buccheri et al. 1996; Lilenbaum 2006). Performance status has long been recognized as an independent prognostic factor for survival, thus patients with a PS2 have typically been excluded from clinical trials in lung cancer (Stanley 1980; Brundage et al. 2002). More recent phase II and III clinical studies dedicated to defining the optimal therapeutic strategy in PS2 patients have demonstrated a significant survival advantage with platinum-based doublet chemotherapy over single agent therapy with pemetrexed, paclitaxel or erlotinib in the 1st line treatment of advanced NSCLC (Lilenbaum et al. 2005; Lilenbaum et al. 2008; Zukin et al. 2013). Despite these data, platinum-based therapy in NSCLC patients with marginal performance status has not been universally adopted due to the perceived burden of excess toxicity associated with therapy (West 2013).

This is a single-arm phase II clinical trial evaluating the safety and efficacy of the PD-L1 inhibitor durvalumab as first-line therapy in 50 patients with advanced NSCLC and ECOG PS2. We hypothesize that PD-L1 inhibition with durvalumab is a safe and tolerable regimen and associated with a survival advantage in PS2 patients with advanced NSCLC. The results of this clinical study may reframe the treatment paradigm of advanced NSCLC patients with a PS2 to focus on immune modulation.

3. PATIENT SELECTION

3.1 Inclusion Criteria

1. Written informed consent and any locally-required authorization (e.g., HIPAA) obtained from the subject prior to performing any protocol-related procedures, including screening evaluations
2. Patients must have histologically or cytologically confirmed Stage IIIB or IV (American Joint Committee on Cancer, 7th edition; AJCC 7) non-small cell lung cancer.
3. Patients must have measurable disease, defined as at least one lesion that can be accurately measured in at least one dimension (longest diameter to be recorded for non-nodal lesions and short axis for nodal lesions) as ≥ 20 mm with conventional techniques or as ≥ 10 mm with spiral CT scan, MRI, or calipers by clinical exam. See Section 12 for the evaluation of measurable disease.

4. Patients must have not have received any prior therapy (chemotherapy, immunotherapy, endocrine therapy, targeted therapy, biologic therapy, tumor embolization, monoclonal antibodies, other investigational agent) for the treatment of stage IV NSCLC. Patients may have received prior adjuvant or neoadjuvant chemotherapy or chemotherapy given as part of a curative intent chemoradiotherapy approach for NSCLC, if the last administration of the prior regimens occurred at least 1 year prior to study entry.
5. Age \geq 18 years at time of study entry.

Because no dosing or adverse event data are currently available on the use of durvalumab in patients <18 years of age, children are excluded from this study.

6. ECOG performance status of 2 (Appendix A).
7. Life expectancy of greater than 12 weeks.
8. Tissue available (archived or fresh tumor biopsy) for the PD-L1 assay.
9. Patients must have normal organ and marrow function as defined below:
 - Absolute neutrophil count (ANC) $\geq 1.5 \times 10^9/L$ (> 1500 per mm^3)
 - Hemoglobin ≥ 9.0 g/dL
 - Platelet count $\geq 100 \times 10^9/L$ ($>100,000$ per mm^3)
 - Serum bilirubin ≤ 1.5 x institutional upper limit of normal (ULN). This will not apply to subjects with confirmed Gilbert's syndrome (persistent or recurrent hyperbilirubinemia that is predominantly unconjugated in the absence of hemolysis or hepatic pathology), who will be allowed only in consultation with their physician.
 - AST (SGOT)/ALT (SGPT) ≤ 2.5 x institutional upper limit of normal unless liver metastases are present, in which case it must be ≤ 5 x ULN
 - Serum creatinine $CL > 30$ mL/min by the Cockcroft-Gault formula (Cockcroft and Gault 1976) or by 24-hour urine collection for determination of creatinine clearance:

Males:

$$\text{Creatinine CL (mL/min)} = \frac{\text{Weight (kg)} \times (140 - \text{Age})}{72 \times \text{serum creatinine (mg/dL)}}$$

Females:

$$\text{Creatinine CL (mL/min)} = \frac{\text{Weight (kg)} \times (140 - \text{Age})}{72 \times \text{serum creatinine (mg/dL)}} \times 0.85$$

10. Female subjects must either be of non-reproductive potential (ie, post-menopausal by history: ≥ 60 years old and no menses for ≥ 1 year without an alternative medical cause; OR history of hysterectomy, OR history of bilateral tubal ligation, OR history of bilateral oophorectomy) OR must have a negative serum pregnancy test upon study entry.
11. The effects of durvalumab on the developing human fetus are unknown. For this reason and because immunomodulatory agents are potentially teratogenic, sexually active women of child-bearing potential and men must agree to use adequate contraception (2 methods of effective contraception from screening) from screening, for the duration of study participation, and for at least 90 days following the last infusion of durvalumab (Section 6.2); cessation of contraception after this point should be discussed with a responsible physician. Periodic abstinence, the rhythm method, and the withdrawal method are not acceptable methods of birth control. Should a woman become pregnant or suspect she is pregnant while she or her partner is participating in this study, she should inform her treating physician immediately.
12. Subject is willing and able to comply with the protocol for the duration of the study including undergoing treatment and scheduled visits and examinations including follow up.

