12.1.1 Definitions

Evaluable for toxicity. All patients will be evaluable for toxicity from the time of their first treatment with durvalumab.

Evaluable for objective response. Only those patients who have measurable disease present at baseline, have received at least one cycle of therapy, and have had their disease re-evaluated will be considered evaluable for response. These patients will have their response classified according to the definitions stated below. (Note: Patients who exhibit objective disease progression prior to the end of cycle 1 will also be considered evaluable.)

Evaluable Non-Target Disease Response. Patients who have lesions present at baseline that are evaluable but do not meet the definitions of measurable disease, have received at least one cycle of therapy, and have had their disease re-evaluated will be considered evaluable for non-target disease. The response assessment is based on the presence, absence, or unequivocal progression of the lesions.

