12.1.2 Disease Parameters

Measurable disease. Measurable lesions are defined as those that can be accurately measured in at least one dimension (longest diameter to be recorded) as ≥ 20 mm by chest x-ray or as ≥ 10 mm with CT scan, MRI, or calipers by clinical exam. All tumor measurements must be recorded in millimeters (or decimal fractions of centimeters).

Note: Tumor lesions that are situated in a previously irradiated area might or might not be considered measurable.

Malignant lymph nodes. To be considered pathologically enlarged and measurable, a lymph node must be ≥ 15 mm in short axis when assessed by CT scan (CT scan slice thickness recommended to be no greater than 5 mm). At baseline and in follow-up, only the short axis will be measured and followed.

Non-measurable disease. All other lesions (or sites of disease), including small lesions (longest diameter <10 mm or pathological lymph nodes with ≥ 10 to <15 mm short axis), are considered non-measurable disease. Bone lesions, leptomeningeal disease, ascites, pleural/pericardial effusions, lymphangitis cutis/pulmonitis, inflammatory breast disease, and abdominal masses (not followed by CT or MRI), are considered as non-measurable.

Note: Cystic lesions that meet the criteria for radiographically defined simple cysts should not be considered as malignant lesions (neither measurable nor non-measurable) since they are, by definition, simple cysts.

‘Cystic lesions’ thought to represent cystic metastases can be considered as measurable lesions, if they meet the definition of measurability described above. However, if non-cystic lesions are present in the same patient, these are preferred for selection as target lesions.

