Target lesions. All measurable lesions up to a maximum of 2 lesions per organ and 5 lesions in total, representative of all involved organs, should be identified as **target lesions** and recorded and measured at baseline. Target lesions should be selected on the basis of their size (lesions with the longest diameter), be representative of all involved organs, but in addition should be those that lend themselves to reproducible repeated measurements. It may be the case that, on occasion, the largest lesion does not lend itself to reproducible measurement in which circumstance the next largest lesion which can be measured reproducibly should be selected. A sum of the diameters (longest for non-nodal lesions, short axis for nodal lesions) for all target lesions will be calculated and reported as the baseline sum diameters. If lymph nodes are to be included in the sum, then only the short axis is added into the sum. The baseline sum diameters will be used as reference to further characterize any objective tumor regression in the measurable dimension of the disease.

Non-target lesions. All other lesions (or sites of disease) including any measurable lesions over and above the 5 target lesions should be identified as **non-target lesions** and should also be recorded at baseline. Measurements of these lesions are not required, but the presence, absence, or in rare cases unequivocal progression of each should be noted throughout follow-up.

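### Inclusion criterion 3 accepts a lymph node of 10 mm short axis on CT as measurable disease, but Section 12.1.2 requires 15 mm, so a patient can be enrolled with no target lesion for the ORR endpoint

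*Combined protocol and SAP*

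**What the plan says.** Section 3.1, item 3, requires at least one measurable lesion and gives its own definition. The dimension depends on the lesion type: "longest diameter to be recorded for non-nodal lesions and short axis for nodal lesions". The size rule follows in the same sentence: "as ≥ 20 mm with conventional techniques or as ≥ 10 mm with spiral CT scan, MRI, or calipers by clinical exam". No different number is given for nodes. The item ends with a pointer: "See Section 12 for the evaluation of measurable disease".

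Section 12.1.2 repeats a similar general rule and then treats nodes separately. To count as measurable, "a lymph node must be ≥ 15 mm in short axis when assessed by CT scan". Smaller nodes are classified explicitly: "pathological lymph nodes with ≥ 10 to <15 mm short axis), are considered non-measurable disease". Target lesions are drawn from the measurable ones: "All measurable lesions up to a maximum of 2 lesions per organ and 5 lesions in total".

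Section 12.1.1 limits evaluability for objective response: "Only those patients who have measurable disease present at baseline", with further conditions on treatment and reassessment. It has a separate category for patients with non-target disease only.

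Section 12.1.3 accepts superficial clinical lesions, with palpable lymph nodes among its examples, as measurable from 10 mm by calipers.

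Section 14.3 estimates ORR with a 90% Wilson score interval, overall and by PD-L1 status. Section 14.2 defines the safety and efficacy cohorts without reference to measurable disease.

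**The concern.** A CT-measured node with a short axis of 12 mm is measurable when eligibility is checked and non-measurable when response is assessed. A site that applies item 3 as written can enrol a patient who has nothing else to measure. Requiring measurable disease at entry is meant to ensure that every patient can be assessed for ORR, and here it does not.

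What is at stake is how such patients enter the ORR. They could be left out of the denominator, kept in it as non-responders, or rated by the non-measurable rules. The choice would be made after the data are seen, in a single-arm trial that also reports ORR in PD-L1 subgroups, where each patient weighs more than in the full 50.

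**Working it through.** **1. The same node under each rule (short axis 10 to under 15 mm, measured on CT, no other measurable lesion)**

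| Question | Section | Answer |
|---|---|---|
| Measurable for entry? | 3.1, item 3 | Yes, at least 10 mm |
| Measurable for response? | 12.1.2 | No, below 15 mm |
| Can it be a target lesion? | 12.1.2 | No |
| Evaluable for objective response? | 12.1.1 | No |
| Which response table fits? | 12.1.4.3 | Non-measurable disease: CR, non-CR/non-PD, not evaluated, PD |
| Is PR possible? | 12.1.4.3 | No such row |
| Is CR possible? | 12.1.4.1, 12.1.4.2 | Yes, if the node falls below 10 mm, any other non-target disease disappears and tumor markers are normal |

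**2. How much shrinkage the nodal part of CR needs**

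For a starting short axis of s mm, the decrease needed to reach 10 mm is (s − 10)/s, and CR needs slightly more.

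- s = 10: 0/10 = 0%, so any shrinkage is enough.
- s = 12: 2/12 = 16.7%.
- s = 14: 4/14 = 28.6%.

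PR in target lesions needs a decrease of at least 30% (Section 12.1.4.1). The two meet at s = 10/0.7 = 14.3 mm. Below that size, the nodal CR condition needs less shrinkage than a target-lesion PR.

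**3. Size of the effect on ORR**

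The plan states no figure that depends on this point. As a check on the interval formula, take its 90% CI of 21% to 41% for a 30% adverse event rate in n = 50 (Section 14.3). With z = 1.645, the Wilson limits are

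[p + z²/(2n) ± z·√(p(1 − p)/n + z²/(4n²))] / (1 + z²/n).

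For p = 15/50 this gives 20.6% to 41.5% (41.46% before rounding), which agrees with the plan.

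Inputs for the illustration: N = 50 (Section 2.3). Two inputs are assumptions, because the documents give neither: 10 responders among the other patients, and k affected patients.

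| k | Kept as non-responders | Dropped as not evaluable | Kept and all rated CR |
|---|---|---|---|
| 1 | 10/50 = 20.0% | 10/49 = 20.4% | 11/50 = 22.0% |
| 3 | 10/50 = 20.0% | 10/47 = 21.3% | 13/50 = 26.0% |
| 5 | 10/50 = 20.0% | 10/45 = 22.2% | 15/50 = 30.0% |

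The last column is an upper extreme. For scale, the 90% Wilson interval for 10/50 is 12.3% to 30.7%, and for 13/50 it is 17.2% to 37.2%.

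**The case against.** The best defence is that item 3 sends the reader to Section 12. On that reading item 3 restates the general size rule, its parenthesis only says which axis to record, and Section 12.1.2 adds the specific nodal rule. A careful site that read both would probably apply 15 mm. This reduces the likely number of affected patients but does not remove the conflict. Item 3 gives a complete definition, names nodes and their short axis within it, and refers to Section 12 for evaluation. It neither withdraws the 10 mm figure nor says which number governs.

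It is also fair to say that Section 12 does classify these patients: not evaluable for objective response, with a separate non-target category. Nor is the lack of a named ORR denominator in Section 14 caused by the nodal threshold, so correcting item 3 would not supply one. Both points stand.

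Three stronger readings are tempting, and the documents do not support them.

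- A reader might infer that these patients are bound to be non-responders. The non-measurable table has a CR row, so they are not.
- A reader might infer that each such patient shifts ORR by 2 percentage points, because 1/50 = 2%. Dropping one non-responder moves 10/50 to 10/49, which is 0.4 points. A shift of 2 points occurs only if the patient is counted as a responder.
- A reader might infer that Section 12 demands 15 mm for every node. Its 15 mm is stated for CT, and Section 12.1.3 accepts palpable nodes from 10 mm by calipers.

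**Conclusion.** The inconsistency is real and lies in the current text. As written, the entry rule admits patients who have no target lesion and are not evaluable for objective response. The point is minor. It concerns only patients whose sole qualifying lesion is a node of 10 to under 15 mm on CT. In stage IIIB or IV disease these are probably few, but that is a judgement, since the documents give no frequency.

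Only ORR, a secondary endpoint, is affected. Overall survival, the safety endpoint, the sample size of 50 and the power statement do not depend on it. The direction of the effect depends on handling. Relative to keeping these patients as non-responders, dropping them raises ORR slightly (20.0% to 21.3% for an assumed three), and rating them CR raises it more (to at most 26.0% in the same example). If they are kept but cannot be rated PR, ORR may instead be too low. In the three-patient example every one of these values lies inside the 90% interval for 10/50.

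**What to change.** In inclusion criterion 3, state the CT threshold for nodes separately so that it matches Section 12.1.2 (at least 15 mm short axis), and keep 10 mm for non-nodal lesions. In the same edit, reconcile the wording with Section 12.1.3 for palpable nodes measured by calipers, and say which threshold applies to nodes measured by MRI. Without this, a blanket 15 mm rule for nodes would create a new conflict with Section 12.1.3.

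In Section 14.3, state whether any patient already enrolled on a node of 10 to under 15 mm is in the ORR denominator and, if so, how that patient's response is rated. If accrual has closed, this is the part that still has practical effect.

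The cost is a phrase in the eligibility criterion, a matching clarification in Section 12 and a sentence in Section 14. The downside is that a patient with no measurable lesion other than such a node would no longer qualify. The documents do not allow an estimate of how many that would be.

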3.2 Exclusion Criteria

1. Involvement in the planning and/or conduct of the study (applies to both AstraZeneca staff and/or staff at the study site). Previous enrollment in the present study.
2. Participation in another clinical study with an investigational product for cancer during the last 12 months.
3. Any previous treatment with a PD1 or PD-L1 inhibitor, including durvalumab.
4. Symptomatic or uncontrolled brain metastases requiring concurrent treatment, inclusive of but not limited to surgery, radiation and/or corticosteroids, in excess of prednisone 10 mg/d or equivalent.
5. Sensitizing mutations in *EGFR* or rearrangements in *ALK* or *ROS1*.
6. History of allergic reactions attributed to compounds of similar chemical or biologic composition to durvalumab.
7. Current or prior use of immunosuppressive medication within 28 days before the first dose of durvalumab, with the exceptions of intranasal and inhaled corticosteroids. Patients may be on systemic corticosteroids provided the dose does not exceed prednisone 10 mg/d or equivalent for 1 week prior to study drug administration.

HCC #:16-054

Version Date: 008/11/2020

8. Active autoimmune disease requiring systemic treatment within the past 2 years.
NOTE: Subjects with autoimmune disease, such as vitiligo, Grave's disease, or psoriasis not requiring systemic treatment (within the past 2 years) are not excluded.
9. Active or prior documented inflammatory bowel disease (e.g., Crohn's disease, ulcerative colitis).
10. History of primary immunodeficiency.
11. History of allogeneic organ transplant.
12. Uncontrolled intercurrent illness including, but not limited to, ongoing or active infection, symptomatic congestive heart failure, uncontrolled hypertension, unstable angina pectoris, cardiac arrhythmia, active peptic ulcer disease or gastritis, active bleeding diatheses including any subject known to have evidence of acute or chronic hepatitis B, hepatitis C or human immunodeficiency virus (HIV), or psychiatric illness/social situations that would limit compliance with study requirements or compromise the ability of the subject to give written informed consent.
13. Known history of previous clinical diagnosis of tuberculosis.
14. History of leptomeningeal carcinomatosis.
15. Receipt of live attenuated vaccination within 30 days prior to study entry or within 30 days of receiving durvalumab.

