14. STATISTICAL CONSIDERATIONS

14.1 Rationale for study design and sample size

Although platinum-based doublet chemotherapy demonstrates a survival advantage over single agent therapy with pemetrexed, paclitaxel or erlotinib in the 1st line treatment of advanced NSCLC with ECOG PS2 (Lilenbaum et al. 2005; Lilenbaum et al. 2008; Zukin et al. 2013), it has not been universally adopted due to the perceived burden of excess toxicity associated with therapy (West 2013). Our study investigates a possible therapy to address the unmet need of an effective, tolerable first-line therapy for the large population of advanced NSCLC patients with PS2. Durvalumab is in the class of PD-L1 monoclonal antibodies that have yielded durable responses in a sizeable minority of patients, without the side effects of a platinum doublet. A single-arm trial is appropriate given the development stage of durvalumab and the incremental steps required toward staging a much larger trial, such as to assess noninferiority with a platinum-based doublet. The trials cited above in this patient population establish benchmarks for reasonable and unreasonable efficacy and toxicity.

Prior phase II/III clinical trials have demonstrated a median OS of about 5 months with single agent therapy in PS2 patients with advanced NSCLC (Lilenbaum et al. 2005; Lilenbaum et al. 2008; Zukin et al. 2013). A median OS of 9 months with durvalumab (approximately the level achieved by the platinum-based doublets in these trials) would demonstrate a clinically meaningful improvement over the historical control median OS of 5 months with single agent therapy. Assuming 18 months of accrual with 6 months of follow-up, N=50 patients are required to have 85% power for a 90% confidence interval for median survival to exclude 5 months (and 78% power for a 95% confidence interval).

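### The prior-therapy ban names only stage IV although stage IIIB is also enrolled, so the eligibility rules do not secure the stated first-line advanced population

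*Combined protocol and SAP*

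**What the plan says.** Four parts of the combined protocol and SAP bear on this.

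- **Stage.** Section 3.1, item 2, requires "histologically or cytologically confirmed Stage IIIB or IV" disease (AJCC 7) and adds no condition on suitability for curative-intent treatment.
- **Prior therapy.** Section 3.1, item 4, lists the barred classes and ends the ban with "monoclonal antibodies, other investigational agent) for the treatment of stage IV NSCLC". Its second sentence allows earlier adjuvant or neoadjuvant chemotherapy, and chemotherapy within curative-intent chemoradiotherapy, but only "if the last administration of the prior regimens occurred at least 1 year prior to study entry".
- **Intended population.** Section 2.3 describes "durvalumab as first-line therapy in 50 patients with advanced NSCLC and ECOG PS2". The Synopsis says the same under Study Design.
- **Yardstick.** Section 14.1 sets OS against a "historical control median OS of 5 months with single agent therapy". Section 14.3 calls the drug promising if the estimated median OS is at least 9 months and/or the lower 90% confidence bound exceeds 5 months. Current stage is tabulated there, but no OS analysis by stage is planned.

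**The concern.** Items 2 and 4 cover different disease. For a patient who enters with stage IIIB and has never had stage IV disease, the ban in item 4 has nothing to act on. Two kinds of patient then pass the written criteria.

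- (a) A stage IIIB patient who recently had non-curative systemic therapy for that stage. This patient is not first-line.
- (b) An untreated stage IIIB patient who could still be offered curative-intent treatment. Item 4 acknowledges that such an approach exists, yet no criterion says whether these patients belong in the trial.

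With no control arm, the comparison with 5 months relies on the enrolled patients resembling those behind the benchmark. Patients of type (b) would tend to raise OS whatever the drug does, and patients of type (a) could lower it. The planned analysis could not separate such a shift in case mix from a drug effect. For type (b) there is also a patient-protection question: whether someone with a curative-intent option should enter a single-agent phase II trial is left unstated.

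**Working it through.** **Step 1. The two patients against the criteria.**

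| Criterion | (a) IIIB, recent non-curative systemic therapy | (b) IIIB, untreated, curative-intent option |
|---|---|---|
| Inclusion 2 (stage IIIB or IV) | passes | passes |
| Inclusion 4, ban (stage IV therapy) | not caught | not caught |
| Inclusion 4, 1-year limit (adjuvant, neoadjuvant, curative-intent regimens) | not caught; regimen is none of these | not applicable |
| Exclusion 2 (investigational cancer study in last 12 months) | not caught if therapy was standard | not caught |
| Exclusion 3 ("Any previous treatment with a PD1 or PD-L1 inhibitor, including durvalumab") | not caught if therapy was chemotherapy | not caught |
| Exclusion 16 (investigator's opinion) | discretionary; silent on prior lines | discretionary; silent on curative options |

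No criterion expressly stops either patient.

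**Step 2. The plan's own power figures.** Inputs from Sections 14.1 and 14.3: N = 50, 18 months of accrual, 6 months of follow-up, medians of 5 and 9 months, Kaplan-Meier with Greenwood variance on log survival. Exponential survival and uniform accrual are assumed. With 10,000 simulated trials, power at a 9-month median is 85.2% for the 90% interval (stated 85%) and 78.4% for the 95% interval (stated 78%). If the true median is 5 months, the Section 14.3 rule is met 6.0% of the time. The sample-size calculation reproduces.

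**Step 3. Could case mix matter? Illustration only.** Let *f* be the stage IIIB share and *m* its median. Suppose the drug is inactive, stage IV has a 5-month median, and the benchmark contains no such patients. The mixture median *t* solves

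(1 − f) · 2^(−t/5) + f · 2^(−t/m) = 0.5.

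For f = 0.2 and m = 12, at t = 5.82: 0.8 × 0.446 + 0.2 × 0.715 = 0.357 + 0.143 = 0.500.

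Each cell gives the mixture median in months, then the chance of meeting either limb of the Section 14.3 rule (4,000 trials per cell):

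| Stage IIIB share | m = 9 | m = 12 | m = 18 | m = 24 |
|---|---|---|---|---|
| 10% | 5.3; 9% | 5.4; 12% | 5.5; 13% | 5.6; 14% |
| 20% | 5.6; 14% | 5.8; 19% | 6.1; 27% | 6.3; 30% |
| 30% | 5.9; 21% | 6.3; 29% | 6.9; 43% | 7.2; 51% |
| 40% | 6.2; 29% | 6.9; 46% | 7.8; 64% | 8.4; 73% |

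The documents give neither *f* nor *m*. The table also treats every stage IIIB patient as long-surviving, which is wider than type (b). If only 2% to 5% of the cohort were of type (b), with m = 12 to 20, the mixture median is 5.1 to 5.3 months and the chance that the 90% interval excludes 5 months is about 7% to 9%, against about 6%. Type (a) patients are not modelled; they would pull the other way.

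**The case against.** The case against has several parts.

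- **Evident intent.** The study is called first-line, and the list of permitted prior regimens with its 1-year limit would make little sense if recent non-curative therapy for stage IIIB were freely allowed. Under Section 4.2 the coordination team and the treating physician investigator confirm eligibility, and exclusion 16 gives the investigator discretion. This makes type (a) enrolment less likely. It does not stand as an answer to the text, because eligibility is confirmed against written criteria that do not say this.
- **Few candidates.** PS2 patients are often not considered fit for intensive treatment; the protocol notes that even platinum doublets are not universally adopted in them. Type (b) may therefore be rare. That is plausible, and it is why the larger entries in the table should not be read as expected error rates.
- **Modest claims.** The primary objective is estimation, the result is to be read alongside safety and durable responses, and stage is tabulated, so the mix will be visible. This stands, but a tabulated mix without OS by stage does not show what the mix did to the median.

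A reader might go further and infer that OS in this trial is not comparable with the 5-month benchmark, or that the false-positive rate is inflated. The documents support neither. Section 14.1 also describes the benchmark patients only as PS2 with advanced NSCLC and gives neither their stage mix nor their prior-therapy rules. If those trials enrolled similar stage IIIB patients, the imbalance shrinks or disappears.

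**Conclusion.** Wrong as written: the eligibility rule is inconsistent with the stated population. Items 2 and 4 do not match, no other criterion closes the gap, and the position of stage IIIB patients with a curative-intent option is not stated. This rests on the text alone and needs no assumption.

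The consequence for OS is more limited. Comparability with the 5-month median is not assured and cannot be checked from the documents. Its size cannot be computed, because the stage IIIB share, stage IIIB survival and the benchmark's stage mix are all missing. Its direction is uncertain, because the two kinds of patient push OS opposite ways. The simulated figures show only that case mix is capable of mattering under a fixed single-arm threshold. Nothing here points to an error in the sample size.

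**What to change.** 1. In inclusion 4, widen the disease named in the ban from stage IV to stage IIIB or IV (advanced) NSCLC. Keep the adjuvant, neoadjuvant and curative-intent allowance with its 1-year limit.
2. Reconcile inclusion 2 with the first-line advanced population: the sponsor should state whether stage IIIB patients must be unsuitable for curative-intent treatment.
3. In Section 14.3, add OS for stage IV alone as a supportive analysis, using the stage data already tabulated, and list prior therapy for stage IIIB patients.
4. In Section 14.1, give the stage mix of the benchmark trials if it is known.

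The cost is two eligibility wording changes, one supportive estimate and one listing. A few stage IIIB patients may no longer be eligible, and the stage IV estimate will be slightly less precise than the full-cohort one. If enrolment is already complete, item 3 is still feasible.
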